6.7.1.2. Folic Acid, Vitamin B12, or Iron Deficiencies

Participants who are noted to be deficient in folic acid, vitamin B12, or iron should have replacement determined by the investigator as per current standard of care.

6.7.1.3. Vaccinations

Participants who elect to receive the COVID-19 vaccine during the study should stop study drug 5 days before and for 10 days after administration of the vaccine. For other non-live vaccines, investigators should consult with the sponsor medical monitor before administration.

6.7.1.4. Corticosteroids

Continued use of systemic corticosteroid (prednisone or equivalent) doses \leq 40 mg/day is permitted through the EOT visit as long as the dose has been stable for at least 14 days prior to randomization.

Prednisone (or equivalent) may be tapered if the investigator considers it appropriate based on the participant's clinical response. The recommended taper schedule is detailed in Table 10.

Table 10: Tapering Guidelines for Corticosteroids

Current Dose of Prednisone	Taper Schedule
> 20 mg QD	Taper by 10 mg every 7 days until a 20 mg daily dose is achieved in participants with a hemoglobin > 10 g/dL with at least a 2 g/dL increase from Day 1.
20 mg QD	Taper by 5 mg every 14 days from 20 mg to 10 mg QD in participants with a hemoglobin > 10 g/dL with at least a 2 g/dL increase from Day 1.
10 mg QD	Taper by 2.5 mg every 14 days from 10 mg to 5 mg in participants with a hemoglobin > 10 g/dL with at least a 2 g/dL increase from Day 1.
5 mg QD	Stop prednisone after 14 days in participants with a hemoglobin > 10 g/dL with at least a 2 g/dL increase from Day 1.
	Note: Tapering may proceed according to the clinical judgement of the investigator.

See Section 6.7.4 for use of corticosteroids as rescue treatment.

6.7.2. Restricted Medications and Procedures

Restricted medications and procedures include the following:

- Short courses (approximately 2 weeks) of high-dose systemic corticosteroid (doses > 40 mg/day prednisone or equivalent) are permitted (eg, for the treatment of severe or life-threatening AEs or non-wAIHA limited related conditions) but are otherwise discouraged from the screening visit through the EOT visit.
- Use of weak inducers of CYP3A4 or weak or moderate inhibitors of CYP3A4 or use of P-glycoprotein substrates is discouraged, and investigators should seek other options where possible (see Appendix E).

6.7.3. Prohibited Medications and Procedures

Prohibited medications and procedures include the following:

- Use of moderate or potent inducers of CYP3A4 and potent inhibitors of CYP3A4 is prohibited, with the exception of topical ketoconazole because of its low bioavailability.
- Apart from the study treatments, the use of any medications as described in the exclusion criteria (see Section 5.2) through the post-treatment follow-up is prohibited.
 - If rituximab is required, the participant must discontinue from study treatment.
- Exposure to a live vaccine within 30 days of randomization through 3 months after the last dose of study drug is prohibited.

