 - *Note:* HIV screening test is optional for participants enrolled in the United States, but participants with known HIV infection enrolled in the United States will be excluded.
- 9. History or presence of an abnormal ECG that, in the investigator's opinion, is clinically meaningful. Participants with screening QTc interval > 470 milliseconds for males and > 480 milliseconds for females (corrected by Fridericia) are excluded. In the event that a single QTcF is > 470 milliseconds for males or > 480 milliseconds for females, the participant may enroll if the average QTcF for triplicate ECGs is < 470 milliseconds for males or < 480 milliseconds for females.
- 10. Use of the following medications:
 - a. Treatment with rituximab within 6 weeks of randomization.
 - b. Use of immunosuppressive therapy within 28 days of the randomization. Immunosuppressive therapy includes, but is not limited to, cyclosporine A, azathioprine, mycophenolate mofetil, or cyclophosphamide.
 Note: Participants receiving corticosteroids must be at a stable dose level (no change in daily dose) ≤ 40 mg/day (prednisone or equivalent corticosteroid dose) for at least 14 days prior to randomization.
 - c. Use of IVIG or erythropoietin within 2 weeks of randomization.
 - d. Chronic or current active infectious disease requiring systemic antibiotics, antifungal, or antiviral treatment or exposure to a live vaccine within 30 days of randomization.
 - e. Use or expected use during the study of any prohibited medications (see Section 6.7.3), including potent CYP3A4 inhibitors or moderate or potent CYP3A4 inducers, within 14 days or 5 half-lives (whichever is longer) before randomization (see Appendix E).
- 11. Current treatment or treatment within 30 days or 5 half-lives (whichever is longer) before randomization with another investigational medication, or current enrollment in another investigational drug and/or device protocol.
- 12. Known hypersensitivity or severe reaction to parsaclisib or its excipients (IB).
- 13. Unable to swallow oral medication, malabsorption syndrome, disease significantly affecting gastrointestinal function, total resection of the stomach or small bowel, ulcerative colitis, symptomatic inflammatory bowel disease, or partial or complete bowel obstruction.
- 14. Current alcohol or drug use that, in the opinion of the investigator, will interfere with the participant's ability to comply with the dose regimen and study evaluations.

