6.7.4. Rescue Treatment

Given the natural history of wAIHA, participants may require supportive care for hemoglobin during the study. Rescue medications may be permitted to serve as a bridging strategy to allow time for study drug to affect hemoglobin. Rescue medication will be prescribed by the investigator and obtained locally. Rescue medication should be considered if the absolute hemoglobin level continues to decline, there is a > 1 g/dL decrease in hemoglobin from the prior assessment, or the participant develops new or worsening symptoms of wAIHA. The following protocol-permitted rescue medications may be used during the study:

- New or increased dose of corticosteroids (prednisone or equivalent) from Day 1 dose
- Transfusions
- IVIG
- Erythropoietin

The date of rescue medication administration as well as the name and dose regimen of the rescue medication must be recorded in the eCRF.

Participants who continue to receive rescue treatment after Week 6 will be considered nonresponders in the primary efficacy analysis, but may continue in the study at the discretion of the investigator.

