7. DISCONTINUATION OF STUDY TREATMENT AND PARTICIPANT WITHDRAWAL

7.1. Discontinuation of Study Treatment

7.1.1. Reasons for Discontinuation

Participants **must** be discontinued from study treatment for the following reasons:

- The participant becomes pregnant.
- Informed consent is withdrawn.

Note: Consent withdrawn means that the participant has explicitly indicated that they do not want to be followed any longer; in this case no further data, except data in public domain, may be solicited from or collected on the participant. Participants may choose to discontinue study treatment and remain in the study to be followed for safety.

- Further participation would be injurious to the participant's health or well-being, in the investigator's medical judgment.
- Unacceptable toxicity as noted in Section 6.5.5.
- Participant has received a prohibited rescue therapy other than those described in Section 6.7.4.
- Participant meets discontinuation criteria as described in Section 6.5.
- The study is terminated by the sponsor.
- The study is terminated by the local health authority, IRB, or IEC.

A participant **may** be discontinued from study treatment as follows:

- If a participant is noncompliant with study procedures or study drug administration in the investigator's opinion, the sponsor should be consulted for instruction on handling the participant.
- If the participant experiences worsening of wAIHA, persistent decline in hemoglobin, or the onset of new wAIHA symptoms requiring treatment.

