10.3. Statistical Analyses

10.3.1. Primary Analysis

The primary analysis will occur after the primary database lock, when the last randomized participant has completed the double-blind treatment period. The primary endpoint is defined as

the proportion of participants attaining durable hemoglobin response, defined as hemoglobin ≥ 10 g/dL with an increase from baseline of ≥ 2 g/dL not attributable to rescue therapy at ≥ 3 of the 4 available visits at Week 12 and/or later during the 24-week double-blind treatment period. The primary analysis will be based on the intent-to-treat population. The primary alternative hypothesis (superiority of parsaclisib 2.5 mg compared with placebo) will be tested using CMH test stratified by stratification factors. The p-value for between-treatment group testing will be compared with 0.05. Odds ratio and corresponding 95% confidence interval will be provided for comparing active and placebo groups. All nonresponders in the double-blind treatment period, as well as all participants who have missing values on the durable response, will be defined as nonresponders for the nonresponder imputation analysis. Participant missing 2 or more values on hemoglobin among the 4 visits will be defined as nonresponders for the primary endpoint. Participants who continue to receive rescue treatment after Week 6 will be considered nonresponders. Summary of the response rates will be reported for the 2 treatment groups. The response rates difference (parsaclisib 2.5 mg – placebo) will be reported along with the 95% confidence interval, which is derived from normal approximation.

Similar analysis will also be performed in the PP population for the primary endpoint. The following deviations are considered major:

- Missing 2 or more hemoglobin values among the 4 visits for the primary endpoint;
- Compliance less than 60%;
- Using prohibited medications or procedures as specified in Section 6.7.3.

Participants with 1 or more such deviations will be excluded from the PP population. In addition, protocol deviations related to inclusion/exclusion criteria, discontinuation criteria, and use of excluded concomitant medications will be evaluated and decided whether they should be excluded. Any exclusion from the PP population will be decided before breaking the blind.

In addition, the following sensitivity analyses may be performed.

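### Protocol 6.7.4 permits IVIG and erythropoietin as rescue, but 6.7.3 prohibits both through exclusion 10c, so permitted rescue can be classed as a deviation and, under 10.3.1, removes the participant from the per-protocol set

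*Protocol*

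**What the plan says.** - **Prohibition.** Protocol 6.7.3: "the use of any medications as described in the exclusion criteria (see Section 5.2) through the post-treatment follow-up is prohibited". The only exemption in that sentence is for the study treatments.
- **What the reference brings in.** Protocol 5.2, criterion 10c: "Use of IVIG or erythropoietin within 2 weeks of randomization".
- **Permission.** Protocol 6.7.4: "The following protocol-permitted rescue medications may be used during the study". The list has four items, and IVIG and erythropoietin are two of them. The section presents rescue as a bridge until study drug can act on hemoglobin.
- **Treatment discontinuation.** Protocol 7.1.1 requires study treatment to stop if "Participant has received a prohibited rescue therapy other than those described in Section 6.7.4".
- **Per-protocol (PP) rule.** Protocol 10.3.1 counts this among the major deviations: "Using prohibited medications or procedures as specified in Section 6.7.3". It adds: "Participants with 1 or more such deviations will be excluded from the PP population".
- **Endpoint rule for rescue.** Protocol 10.3.1: "Participants who continue to receive rescue treatment after Week 6 will be considered nonresponders".
- **Final analysis.** The note that opens Protocol Section 10 passes the final analyses to the SAP. SAP 5.3.1 runs all efficacy analyses on the safety population, and SAP 7 gives no p-values. SAP 6.3 still has protocol deviations summarized and listed, as Table 1.5.3 and Listing 1.1.3 in its Appendix A.

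**The concern.** A site treating an ongoing participant finds the same two drugs banned in one section and permitted in the next. Whoever codes deviations meets the same conflict: rescue given as 6.7.4 allows can be recorded as prohibited medication use.

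The protocol's PP rule carries the conflict into an analysis set. Rescue occurs after randomization and depends on how the participant's hemoglobin is doing. Removing participants for it selects on something close to the outcome, whereas the primary endpoint already has its own rule for rescue. The two rules also cover different people. The endpoint rule makes a participant a nonresponder only if rescue continues after Week 6. The PP rule has no time limit, so it would also remove someone bridged with IVIG before Week 6 who then had a durable response.

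**Working it through.** **Step 1: the passages together.**

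| Place | Status of IVIG and erythropoietin on study | Refers to 6.7.4? |
|---|---|---|
| 5.2, criterion 10c | Excluded within 2 weeks of randomization | No |
| 6.7.3 | Prohibited through post-treatment follow-up, by reference to 5.2 | No |
| 6.7.4 | Permitted as rescue during the study | n/a |
| 7.1.1 | Treated as outside prohibited rescue, for stopping treatment | Yes |
| 10.3.1, PP deviations | Major deviation, by reference to 6.7.3 | No |

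The 2-week window in 10c does not remove the conflict, because 6.7.3 takes the medications named in 5.2 and sets its own period. The exception in 7.1.1 governs discontinuation of treatment and amends neither 6.7.3 nor 10.3.1. Section 10.3.1 also provides for review of further deviations before unblinding, including use of excluded concomitant medications. That review is additional to the listed deviations, which exclude automatically.

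**Step 2: the plan's own figure.** Protocol 10.1 assumes 70% against 25% response with 67 and 33 participants and states power over 90% at 2-sided alpha 0.05. For the chi-square test in its normal approximation:

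- pooled rate = (67 × 0.70 + 33 × 0.25) / 100 = 0.5515
- standard error under the null = √[0.5515 × 0.4485 × (1/67 + 1/33)] = 0.1058
- standard error under the alternative = √(0.70 × 0.30/67 + 0.25 × 0.75/33) = 0.0939
- power = Φ[(0.45 − 1.96 × 0.1058) / 0.0939] = 99.5%

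The statement is reproduced. The contradiction does not depend on it; the two rates are only used in Step 3.

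**Step 3: what PP removal could do.** The documents give no rate of IVIG or erythropoietin rescue, so the shares below are assumptions. Let p be the true response rate in an arm and f the share of its nonresponders removed from PP:

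PP rate = p / [p + (1 − p)(1 − f)]

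Example, parsaclisib with f = 10%: 0.70 / (0.70 + 0.30 × 0.90) = 72.2%. Placebo with f = 30%: 0.25 / (0.25 + 0.75 × 0.70) = 32.3%. The odds ratio is 7.0 × (1 − f placebo) / (1 − f parsaclisib).

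| Nonresponders removed, parsaclisib / placebo | PP rates | Difference, points | Odds ratio |
|---|---|---|---|
| 0% / 0% | 70.0% vs 25.0% | 45.0 | 7.0 |
| 10% / 10% | 72.2% vs 27.0% | 45.1 | 7.0 |
| 30% / 30% | 76.9% vs 32.3% | 44.7 | 7.0 |
| 50% / 50% | 82.4% vs 40.0% | 42.4 | 7.0 |
| 10% / 30% | 72.2% vs 32.3% | 39.9 | 5.4 |
| 30% / 10% | 76.9% vs 27.0% | 49.9 | 9.0 |

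Differences are taken before rounding. With no true effect (25% in both arms), the two unequal patterns give −5.2 and +5.2 points.

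The table removes only nonresponders. Early-rescued responders would be removed as well, which pushes the other way. If 10% of parsaclisib responders and nobody else were removed, the parsaclisib rate would be 0.63 / (0.63 + 0.30) = 67.7% and the difference 42.7 points.

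**The case against.** The strongest reply is that the intent is clear. Section 6.7.4 is the specific rule and calls these drugs permitted, 7.1.1 treats its list as outside prohibited rescue, and 10c is an entry washout. Appendix F records that Amendment 1 moved rituximab out of the rescue section to clarify that it is prohibited, while IVIG and erythropoietin remain on the rescue list. On this view 6.7.3 merely lacks a cross-reference. That is probably the cause, and it lowers the chance that a site is misled. It does not settle the text: the exception is written in 7.1.1 and absent from 6.7.3 and 10.3.1.

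The second reply is that the PP set no longer matters. This largely stands. PP was supportive beside an intent-to-treat primary analysis, and the readable SAP names only the safety population.

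Three stronger readings are tempting, and the documents do not support them:

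- *The PP rule removes treatment failures.* Only rescue continuing after Week 6 makes a participant a nonresponder, so the rule could also remove durable responders.
- *The removed participants are mostly on placebo, so the bias has a known direction.* No rescue rates by arm are given. The design assumptions imply 67 × 0.30 = 20.1 nonresponders on parsaclisib and 33 × 0.75 = 24.75 on placebo, which is not lopsided in number.
- *Permitted rescue will appear as a deviation in the report.* The readable SAP defines no deviation categories, and Protocol 11.3 places deviation handling in monitoring plans that are not among these documents. It can appear there; the text does not say that it will.

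**Conclusion.** The contradiction holds in the current text. Taken literally, 6.7.3 with 10c prohibits two drugs that 6.7.4 permits, and 10.3.1 turns their use into automatic PP exclusion. Two consequences remain live: conflicting instructions for ongoing participants, since the ban runs through follow-up, and uncertain classification in the deviation table and listing.

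The PP consequence is a defect of the protocol's planned analysis and does not threaten the final one, which is descriptive, uses the safety population and covers 13 treated participants. Its size and direction are undetermined. The shift of about 5 points either way rests on assumed removal of 10% and 30% of nonresponders in opposite arms at true rates of 70% and 25%. Equal removal of nonresponders leaves the odds ratio at 7.0. A reader should not infer a bias in favor of either arm.

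**What to change.** 1. Reconcile Protocol 5.2 (10c), 6.7.3, 6.7.4, 7.1.1 and 10.3.1 so that each drug has one status on study. Which drugs are allowed as rescue is for the sponsor's clinical team; this review takes no position.
2. In 10.3.1, state that rescue permitted under the reconciled 6.7.4 does not count as prohibited medication use and is handled by the endpoint's rescue rule.
3. Put the same statement in the deviation specification behind SAP 6.3, so that Table 1.5.3 and Listing 1.1.3 classify such rescue consistently.

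The cost is about one clause in 6.7.3, one in 10.3.1 and one in the deviation specification. No new data or analyses are needed. If the protocol is not amended again, the third step still settles the reporting; the site instructions would then need a written clarification.

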6.7.4. Rescue Treatment

Given the natural history of wAIHA, participants may require supportive care for hemoglobin during the study. Rescue medications may be permitted to serve as a bridging strategy to allow time for study drug to affect hemoglobin. Rescue medication will be prescribed by the investigator and obtained locally. Rescue medication should be considered if the absolute hemoglobin level continues to decline, there is a > 1 g/dL decrease in hemoglobin from the prior assessment, or the participant develops new or worsening symptoms of wAIHA. The following protocol-permitted rescue medications may be used during the study:

- New or increased dose of corticosteroids (prednisone or equivalent) from Day 1 dose
- Transfusions
- IVIG
- Erythropoietin

The date of rescue medication administration as well as the name and dose regimen of the rescue medication must be recorded in the eCRF.

Participants who continue to receive rescue treatment after Week 6 will be considered nonresponders in the primary efficacy analysis, but may continue in the study at the discretion of the investigator.

6.8. Treatment After the End of the Study

Participants who have completed at least 2 months of active study treatment (starting from first dose of parsaclisib) and are receiving benefit will have the option to continue to receive parsaclisib provided within a rollover study or through commercially available supply where applicable.

7. DISCONTINUATION OF STUDY TREATMENT AND PARTICIPANT WITHDRAWAL

7.1. Discontinuation of Study Treatment

7.1.1. Reasons for Discontinuation

Participants **must** be discontinued from study treatment for the following reasons:

- The participant becomes pregnant.
- Informed consent is withdrawn.

Note: Consent withdrawn means that the participant has explicitly indicated that they do not want to be followed any longer; in this case no further data, except data in public domain, may be solicited from or collected on the participant. Participants may choose to discontinue study treatment and remain in the study to be followed for safety.

- Further participation would be injurious to the participant's health or well-being, in the investigator's medical judgment.
- Unacceptable toxicity as noted in Section 6.5.5.
- Participant has received a prohibited rescue therapy other than those described in Section 6.7.4.
- Participant meets discontinuation criteria as described in Section 6.5.
- The study is terminated by the sponsor.
- The study is terminated by the local health authority, IRB, or IEC.

A participant **may** be discontinued from study treatment as follows:

- If a participant is noncompliant with study procedures or study drug administration in the investigator's opinion, the sponsor should be consulted for instruction on handling the participant.
- If the participant experiences worsening of wAIHA, persistent decline in hemoglobin, or the onset of new wAIHA symptoms requiring treatment.

7.1.2. Discontinuation Procedures

In the event that the decision is made to permanently discontinue the study treatment, the EOT visit (EOT1 during the double-blind period, EOT2 during the open-label period, or EOT3 during the long-term extension) should be conducted. The participant will then enter the 12-week post-treatment follow-up period. These visits are described Table 3, Table 4, and Table 5. The last date of the last dose of study drug and the reason for discontinuation of study drug will be recorded in the eCRF.

Note: Upon implementation of Protocol Amendment 2:

- Participants receiving parsaclisib who permanently discontinue study drug will enter the post-treatment follow-up period for 1 visit (FUP1/EOS) approximately 4 weeks after the last dose of study drug.
- Participants receiving placebo who permanently discontinue study drug will no longer be required to enter the post-treatment follow-up period and will perform EOT1/EOS upon discontinuation of treatment.

If a participant is discontinued from study treatment:

- The study monitor or sponsor must be notified.
- The reason(s) for discontinuation must be documented in the participant's medical record and the primary reason for discontinuation must be included in the eCRF.
- The EOT visit should be performed and date recorded.
- The status of the participant should be updated to EOT in the IRT.
- Participants must be followed for safety until the time of the follow-up visit or until study drug—related toxicities resolve, return to Day 1, or are deemed irreversible, whichever is longest.

If the participant discontinues study treatment and actively withdraws consent for collection of follow-up data (safety follow-up or disease assessment), then no additional data collection should occur; however, participants will have the option of withdrawing consent for study treatment but continuing in the follow-up period of the study for safety/efficacy assessments.

